Methodology/Study Design	Open label, prospective, Phase II single arm trial. Patients will receive immunoembolization (IEMBO) every 3 weeks in combination with ipilimumab (IPI) + nivolmuab (NIVO) initially to be given every 3 weeks for 4 doses. Dose of IPI + NIVO will be the reverse lower dose of IPI 1mg/kg every 3 weeks x4 doses and NIVO 3mg/kg every 3 weeks x 4 doses then NIVO flat dose 480mg every 4 weeks. In the event of toxicity during the first four IPI + NIVO + IEMBO combination treatments, IPI and/or NIVO may be dropped at the investigator's discretion and patient can continue on with NIVO + IEMBO or IEMBO alone. Once patient completes the first four doses of combination and moves onto the maintenance NIVO phase, IEMBO will then be given every 4 weeks. In the event of NIVO-related toxicity during this phase, NIVO can be dropped at the investigator's discretion. Initial scans will be performed following two IPI+NIVO and IEMBO treatments, before treatment #3, to ensure no evidence of rapid progression. Initial radiographic response will be determined following all 4 doses of IPI+NIVO and/or NIVO alone if IPI dropped and/or four IEMBO treatments if both IPI and NIVO are dropped. Subsequent scans will be done every two IEMBO treatments. Immune-related side effects will be managed as per protocol. Steroid treatment will be allowed if it is tapered to 5 mg of prednisone or less before initiation of next cycle. Combination treatment could be postponed for up to 10 weeks (from the date of next scheduled treatment). if patients need a treatment break for immune-related toxicity. Safety will also be assessed and the toxicity of the treatment will be monitored using the NCI Common Toxicity Criteria. Immunologic parameters will also be evaluated as detailed in the protocol.
Study Duration	18-24 months to accrue. Subjects will receive study treatment for a maximum of 2 years and will subsequently be followed for a minimum of one year.
Study Center(s)	Thomas Jefferson University Hospital

	Primary Objective: Determine the clinical benefit of combination treatment with IEMBO, Ipilimumab, and Nivolumab.			
Objectives	Secondary Objective(s): 1. Determine all treatment and immune related toxicities 2. Determine PFS 3. Determine OS Exploratory Objective:			
	Determine and correlate clinical response with the degree and change in inflammatory/immune response			
Number of Subjects	35			
Diagnosis and Main Inclusion Criteria	 Inclusion criteria: Histologically confirmed metastatic uveal melanoma in the liver. Patients must have at least one measurable liver metastasis that is ≥ 10 mm in longest diameter by CT scan or MRI. The total volume of the tumors must be less than 50% of the liver volume. Willingness and ability to give informed consent. ECOG performance status of 0, or 1 Adequate renal and bone marrow functions: serum creatinine ≤ 2.0 mg/dl, granulocyte count ≥ 1000/mm3, and platelet count ≥ 100,000/mm3. Adequate liver function: bilirubin ≤ 2.0 mg/ml, albumin ≥ 3.0 g/dl, PT/PTT less than 1.5 times of upper normal limit (UNL), and AST and ALT less than 3.0 and alkaline phosphatase less than 1.5 times of UNL. Age ≥ 18 years of age. 			
Study Therapy, Dose, Route, Regimen	 Recombinant human GM-CSF (Sargramostim, Leukine®, Sanofi US). GM-CSF 1,500 mcg) will be mixed with ethiodized oil (Ethiodol®). The GM-CSF/ethiodized oil mixture will be injected selectively into one of the hepatic lobes. This will be followed by infusion of gelatin sponge particles to achieve the stasis of blood flow (immunoembolization). This will repeat every 3 weeks x 4 then every 4 weeks Ipilimumab (Yervoy) at 1mg/kg every 3 weeks x 4 doses. Nivolumab (Opdivo) at 3mg/kg every 3 weeks x 4, then flat dose 480mg every 4 weeks. 			
Duration of administration and follow-up	Patients will receive combination treatment of immunoembolization, ipilimumab, and nivolumab every 3 weeks for 12 weeks and in patients with CR, PR, and SD at 12 weeks, maintenance therapy with combination immunoembolization and nivolumab every 4 weeks will be offered until disease progression or unacceptable toxicity, for a maximum of 2 years. Follow-up contact will take place every 3 months for minimum of one year or until death to determine clinical status.			

We propose an increase in hepatic metastasis stabilization rate (SD+PR+CR) of 60%, as experienced with IEMBO alone, to 80% with IEMBO + IPI + NIVO. We plan to enroll 35 patients to have a power > 80% (alpha = 0.05) and to detect our proposed response rate. Simon's two-stage design will be used (Minimax). The null hypothesis that the true response rate is 60% will be tested against a one-sided alternative. In the first stage, 13 patients will be accrued. If there are 8 or fewer responses in these 13 patients, the study will be stopped. Otherwise, 22 additional patients will be accrued for a total of 35. The null hypothesis will be rejected if 26 or more responses are observed in 35 patients. This design yields a type I error rate of 0.05 and power of 80% when the true response rate is 80%.

[figure not shown]
Study Schema

- Confirmed metastatic uveal melanomato liver
- ECOG 0-1
- First line systemic immunotherapy
- First line liver directed therapy

Ipilimumab 1mg/kg every 3 weeks x4

Nivolumab 3mg/kg every 3 weeks x4

Patient will continue treatment until maximum clinical benefit and followed for a minimum of one year

1.0 INTRODUCTION

This document is a protocol for a human research study. This study is to be conducted according to US and international standards of Good Clinical Practice (FDA Title 21 part 312 and International Conference on Harmonization guidelines), applicable government regulations and Institutional research policies and procedures.

1.1 Background and Rationale

Uveal melanoma is the most common primary intraocular cancer in adults. Incidence in the United States is four to seven per million people and noted to make up approximately 3% of all melanomas. Despite the availability of effective treatments for primary uveal melanoma, there is no standard adjuvant therapy and up to 50% of patients subsequently develop metastasis. Hepatic involvement is often the first manifestation of systemic disease, and in more than half of patients it remains the only site of metastases. Other sites of metastases include lungs, bones, brain, subcutaneous tissues, peritoneal cavity, and other visceral organs. Survival after liver metastases is reportedly less than 6 months without treatment.

The major challenge in management of metastatic uveal melanoma is the lack of effective treatments. Metastatic uveal melanoma is highly resistant to standard systemic chemotherapies that have been used for metastatic skin melanoma.² A novel approach using a MEK inhibitor showed a modest but improved response (15% RECIST response) in metastatic uveal melanoma.³ However, the progression free survival was short (15.9 weeks) and there was no significant overall survival benefit.

Over the past decade, there have been paradigm-altering advances in cutaneous melanoma due to the advent of effective systemic immunotherapy interventions including immune-checkpoint-pathway blockades such as anti–CTLA-4 antibody (ipilimumab) and anti–PD-1 antibody (pembrolizumab and nivolumab).⁴ Despite encouraging clinical study results in metastatic cutaneous melanoma, these immune checkpoint blockades have not shown dramatic response in metastatic uveal melanoma. Ipilimumab resulted in regression in only 5% of metastatic uveal melanoma patients.^{5,6} On the other hand, toxicity to ipilimumab, especially immune-related toxicity, is considered to be similar to that of metastatic skin melanoma (~30% grade 3 or greater). Published data now for anti-PD1 and anti-PDL1 antibodies when used alone note an approximate 3.6% response rate and 9% stable disease rate.⁷

Since the liver is usually the dominant site of metastasis and hepatic metastasis is life-limiting in the majority of uveal melanoma patients, liver-targeted locoregional treatment is a preferred standard of care since there are no effective systemic treatments available at this time. Considering resistance to standard chemotherapeutic treatment, we have developed a new therapy called Immunoembolization (IEMBO)⁹⁻¹¹. This technique involves embolization of the hepatic artery with gelatin sponge particle in conjunction with administration of granulocyte-macrophage colony stimulating factor (GM-CSF) mixed with ethiodized oil through the tumor-feeding hepatic artery. IEMBO provides several advantages beyond the ischemic damage consequent to bland embolization alone. Some of these advantages include attraction and stimulation of antigen-presenting cells in the hepatic tumor sites and improved uptake of tumor antigens released from necrotic tumor cells. In addition, local stimulation of the immune system may produce a systemic immune response against tumor cells, which thereby suppresses the growth of extrahepatic metastases. This

approach resulted in stabilization of multiple hepatic metastasis in approximately 60% of uveal melanoma patients. Furthermore, this liver-directed treatment induced a systemic response against melanoma, including the development of inflammatory responses in remote metastasis and the prolongation of progression-free survival in extra-hepatic metastasis.⁹⁻¹¹

Due to the low response rate of systemic single agent immune checkpoint inhibitor therapy in metastatic uveal melanoma, we have been combining with IEMBO with systemic ipilimumab as well as pembrolizumab and nivolumab as our institutional standard of care. It is hypothesized that inflammation induced by IEMBO with GM-CSF coupled with systemic immune checkpoint therapy could be synergistic. We have published on our experience with combination IEMBO and ipilimumab. The combination was well tolerated and incidence of serious hepatic toxicity was low. Our experience with IEMBO in combination with anti-PD1 antibodies has been similar.

In cutaneous melanoma the combination of Ipilimumab and Nivolumab over each agent alone has proven to result in improved response rate and deeper responses.¹³ While we do not have data regarding this combination in metastatic uveal melanoma, there is reason to believe that the combination may prove also to be superior to each agent when used alone.

To further enhance local and systemic anti-tumor immune responses, we proposed to investigate the safety and efficacy of IEMBO + Ipilimumab + Nivolumab combination treatment.

2.0 STUDY OBJECTIVES

2.1 Primary Objective: Determine the clinical benefit of combination treatment with IEMBO in combination with Ipilimumab and Nivolumab.

2.2 Secondary Objective:

- a. Determine all treatment and immune related toxicities
- b. Determine progression free survival
- c. Determine overall survival

2.3 Exploratory Objective:

a. Determine and correlate clinical response with the degree and change in inflammatory/immune responses

3.0 STUDY DESIGN

3.1 General Design

This study is an open label, prospective, phase II, two-stage, single arm trial with the potential for improved outcome with treatment of IEMBO in combination with IPI + NIVO. Patients will receive study treatment for a maximum of two years or until disease progression. The design will be a two-stage minimax design using the method of Simon. Choice of design is guided by a desire to stop the trial early if the actual hepatic metastasis stabilization rate is 60% or less. If the stabilization rate rate is 80% or greater, we would like to have a low probability of failing to conclude effective.

Patients will receive IEMBO every 3 weeks in combination with IPI + NIVO initially to be given every 3 weeks for 4 doses. Dose of IPI + NIVO will be the reverse lower dose of IPI 1mg/kg every 3 weeks x4 doses and NIVO 3mg/kg every 3 weeks x 4 doses then NIVO flat dose 480mg every 4 weeks. In the event of toxicity during the first four IPI + NIVO + IEMBO, IPI and/or NIVO may be dropped at the investigator's discretion and patient can continue on with NIVO + IEMBO or IEMBO alone. Once patient completes the first four doses of combination and moves onto the maintenance NIVO phase, IEMBO will then be given every 4 weeks. In the event of NIVO-related toxicity during this phase, NIVO may be dropped at the investigator's discretion and the patient may continue on with IEMBO only, if the investigator feels patient is receiving clinical benefit from it. Initial scans will be performed between cycles 2 and 3 to ensure no evidence of rapid progression. Initial radiographic response will be determined following all 4 doses of IPI+NIVO and/or NIVO alone if IPI dropped, and/or four IEMBO treatments if both IPI and NIVO are dropped. Subsequent scans will be done after every two IEMBO treatments. Immune-related side effects will be managed as per protocol. Steroid treatment will be allowed if it is tapered to 5 mg of prednisone or less before initiation of next cycle. Combination treatment could be postponed for up to 10 weeks (from the date of next scheduled treatment), if patients need a treatment break for immune-related toxicity. Safety will also be assessed and the toxicity of the treatment will be monitored using the NCI Common Toxicity Criteria. Immunologic parameters will also be evaluated as detailed in the protocol.

3.2 Primary Study Endpoint

1. Best hepatic response (CR + PR +SD) by response criteria (RECIST 1.1) starting at week 12

3.3 Secondary Study Endpoints

- 1. All toxicities using the NCI CTCAE Version 4.0.
- 2. Progression Free Survival (hepatic and systemic PFS)
- 3. Overall survival

3.4 Exploratory (Correlative) Endpoints

Systemic and local immune/inflammatory response:

- a. Degree and classification of tumor-infiltrating cells
- b. Presence and changes in PD-L1 expression in tumor and tumor-infiltrating cells
- c. Changes in immune tumor microenvironment (immune gene signature)
- d. Tumor mutational burden prior to treatment
- e. Changes in TCR repertoire analysis (ImmunoSeq)
- f. Changes in cytokine productions (multiplex cytokine assay)
- g. Changes in PBMC cell populations, including T cells and MDS.

4.0 SUBJECT SELECTION AND WITHDRAWAL

4.1 Inclusion Criteria

- Histologically confirmed metastatic uveal melanoma in the liver. Patients must have at least one measurable liver metastasis that is ≥ 10 mm in longest diameter by CT scan or MRI.
- 2. The total volume of the tumors must be less than 50% of the liver volume.
- 3. Willingness and ability to give informed consent.
- 4. Agreement to access archival tissue or agreement for tumor biopsy prior to treatment
- 5. ECOG performance status of 0, or 1
- 6. Adequate renal and bone marrow functions: serum creatinine ≤ 2.0 mg/dl, granulocyte count ≥ 1000/mm3, and platelet count ≥ 100,000/mm3.
- 7. Adequate liver function: bilirubin ≤ 2.0 mg/ml, albumin ≥ 3.0 g/dl, PT/PTT less than 1.5 times normal, AST and ALT less than 3x ULN and alkaline phosphatase less than 1.5 times ULN (grade 1).
- 8. Age \geq 18 years of age.
- 9. Women must not be pregnant or breast-feeding. See section 4.2.1
- 10. Women of child-bearing potential must use at least two other accepted and effective methods of contraception and/or to abstain from sexual intercourse for at least 23 weeks after the last dose of nivolumab and/or ipilimumab and sexually active males must use at least two other accepted and effective methods of contraception and/or to abstain from sexual intercourse for at least 31 weeks after the last dose of nivolumab and/or ipilimumab. See section 4.2.1

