4.2 Exclusion Criteria

- 1. Failure to meet any of the criteria set forth in the Inclusion criteria section
- 2. Previous systemic exposure to anti-CTLA-4 antibody or anti-PD1 antibody
- 3. Previous liver-directed treatments including chemoembolization, radiosphere, hepatic arterial perfusion, or drug-eluting beads; liver resection and focal ablation are permitted.
- 4. Presence of symptomatic liver failure including ascites and hepatic encephalopathy.
- 5. Presence of untreated brain metastases. If patients have had previous treatment for the brain metastasis, an MRI or CT scan of the brain must confirm the stabilization of the brain metastasis for more than 2 months.
- 6. Presence of uncontrolled hypertension or congestive heart failure, or acute myocardial infarction within 6 months of entry.
- 7. Presence of any other medical complication that implies survival of less than six months
- 8. Uncontrolled severe bleeding tendency or active GI bleeding.
- 9. Significant allergic reaction to contrast dye or GM-CSF.
- 10. Immunosuppressive treatments within 4 weeks prior to embolization, unless prednisone ≤ 5mg or equivalent
- 11. Pregnancy or breast-feeding women.
- 12. Patients with active hepatitis with SGOT and SGPT equal or greater than 5 times normal
- 13. Biliary obstruction, biliary stent or prior biliary surgery except cholecystectomy
- 14. Positive for known HIV Infection

- 15. Uncontrolled Chronic Obstructive Pulmonary Disease or previous known pulmonary fibrosis
- 16. Active infection.
- 17. Auto-immune disease including inflammatory bowel disease, lupus, rheumatoid arthritis, but not including hypothyroidism or psoriasis if condition has been stable for 2 months or greater.

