6.1.2 Evaluation during treatment

An interim history and physical examination will be performed prior to each subsequent treatment cycle to assess toxicities and disease status. This is to be done upon admission to the hospital and at outpatient appointments for immunotherapy infusion.

CBC with differential, platelet count, liver function tests and renal function tests and LDH will be done prior to the treatment, day of IEMBO, day after IEMBO and, and then weekly unless more frequently is required. In the event that a subject is no longer receiving infusion on Day 1 (IPI and/or NIVO), and only receiving IEMBO – Day 1 labs (CRP, TSH, & T4) will be drawn prior to IEMBO on Day 2.

Due to possibility of abrupt onset endocrinopathy TSH,ACTH, T3, T4, cortisol will also be ordered as part of monitoring for side effects related to IPI+NIVO and NIVO the week prior to scheduled infusion. On Day 1 of each cycle TSH and T4 will also be ordered.. Lipase will be ordered on as needed basis.

Coagulation tests (PT, PTT, INR) will be done prior to each embolization.

Sixty (60) ml of blood will be drawn for immunological testing prior to each cycle beginning. Additionally, 10 ml of blood will be drawn before, 1 hours and on Day 3 after the individual IEMBO for cytokine measurements. Also up to an additional 10ml of blood will be drawn prior to the initial cycle for purposes of determining tumor mutational load. Study blood will be collected for the first 6 cycles of treatment, then at 12 and 24 months and at End of Treatment visit, even if visit is before the completion of 6th cycle.

Eligibility criteria will be applied to each treatment. Only the patients who fulfill the eligibility criteria will be offered further embolization treatment. If follow-up test results indicate that patients have become ineligible for treatment, the next treatment will be postponed for a maximum of 4 weeks. If sufficient improvement is not seen during this period to restore eligibility for the next treatment, they will be removed from the study.

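### The bilirubin eligibility limit is printed in mg/ml instead of mg/dl, so as written it is 200 mg/dl and excludes no one

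*Combined protocol and SAP*

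**What the plan says.** Section 4.1, criterion 7, opens with "Adequate liver function: bilirubin ≤ 2.0 mg/ml, albumin ≥ 3.0 g/dl" and goes on to limits for PT/PTT, AST and ALT, and alkaline phosphatase. The Study Summary, under Diagnosis and Main Inclusion Criteria, gives the same bilirubin limit in the same unit. Criterion 6, directly above in section 4.1, has "serum creatinine ≤ 2.0 mg/dl".

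Three other provisions determine how the bilirubin limit operates:

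- Section 4.2, exclusion 1, disqualifies a patient for "Failure to meet any of the criteria set forth in the Inclusion criteria section".
- Section 6.1.2 carries the criteria into the treatment period: "Only the patients who fulfill the eligibility criteria will be offered further embolization treatment". If a patient has become ineligible, "the next treatment will be postponed for a maximum of 4 weeks", and removal follows if eligibility is not restored in that time.
- Sections 6.1.5 and 6.1.6 also make continued treatment depend on the eligibility criteria still being met.

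No other section states a bilirubin limit for eligibility, and the revision history in section 15.4 records no change to criterion 7.

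**The concern.** A limit in mg/ml is 100 times looser than the same number in mg/dl. The neighbouring serum limits are per decilitre, and the printed value is far above any bilirubin level the protocol uses elsewhere, so the unit looks like a slip.

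Bilirubin is a basic check on hepatic reserve, and every patient here has liver metastases and is to have repeated hepatic artery embolization. Section 5.1.2 names impaired liver function as a major side effect of ethiodized oil. Section 5.5 warns that the combination may raise the risk of immune hepatitis and other liver toxicity.

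Taken literally, a patient with raised bilirubin who breaches no other hepatic limit or exclusion passes both the entry check and each re-check. The written text is also what an auditor works from, since section 12.2.1 has audits verify that eligibility criteria were met.

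**Working it through.** **Inputs**

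| Item | Value | Source |
|---|---|---|
| Bilirubin limit as printed | ≤ 2.0 mg/ml | Section 4.1 no. 7; Study Summary |
| Creatinine limit | ≤ 2.0 mg/dl | Section 4.1 no. 6 |
| Albumin limit | ≥ 3.0 g/dl | Section 4.1 no. 7 |
| AST/ALT limit | < 3 × ULN | Section 4.1 no. 7 |
| Alkaline phosphatase limit | < 1.5 × ULN | Section 4.1 no. 7 |
| Total bilirubin cut-off for delaying rather than stopping immunotherapy | 5 × ULN | Section 15.3, footnote to the hepatic algorithm |
| Bilirubin ULN | 1.0 to 1.5 mg/dl | Assumption; not in the documents |

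**Step 1: convert the unit.** 2.0 mg/ml × 100 ml/dl = 200 mg/dl. Against 2.0 mg/dl the ratio is 200 / 2.0 = 100. This step needs no assumption.

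**Step 2: test which unit fits the rest of criterion 7.** In multiples of the assumed ULN:

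- Limit in mg/dl: 2.0 / 1.5 = 1.3 to 2.0 / 1.0 = 2.0 × ULN. This is the same order as the adjacent enzyme limits of 3 × and 1.5 × ULN.
- Limit as printed: 200 / 1.5 = 133 to 200 / 1.0 = 200 × ULN.

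**Step 3: compare with the other bilirubin level in the protocol.** Under the same assumption, 5 × ULN is 5 × 1.0 = 5.0 to 5 × 1.5 = 7.5 mg/dl. The printed entry limit is therefore 200 / 7.5 = 27 to 200 / 5.0 = 40 times that level. The two thresholds do different jobs, so this shows scale only.

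**Step 4: establish what remains in force.** Only the bilirubin component is void. Albumin, PT/PTT, AST/ALT and alkaline phosphatase in criterion 7 are unaffected. So are:

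- exclusion 4, "Presence of symptomatic liver failure including ascites and hepatic encephalopathy";
- exclusion 12, "Patients with active hepatitis with SGOT and SGPT equal or greater than 5 times normal";
- exclusion 13, "Biliary obstruction, biliary stent or prior biliary surgery except cholecystectomy".

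The case that slips through is therefore narrow: raised bilirubin with none of these breached. A bilirubin of 4 mg/dl, for instance, is twice the intended limit (4 / 2.0 = 2) but 2% of the printed one (4 / 200 = 0.02).

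**Step 5: check for an effect on the design.** No figure in section 7 is computed from the bilirubin limit, so the two-stage rule and its error rates do not depend on it.

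**The case against.** The strongest reply is that this is a typographical slip of no consequence. The number 2.0 is right, the units beside it settle the meaning, and harm would require site staff to apply a reading nobody thinks was intended. That largely stands. It is why the practical risk is called limited.

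A second reply is that bilirubin is not left unwatched. Section 6.1.2 requires liver function tests before treatment, on the day of embolization, the day after and then weekly, and the schedule in section 15.1 includes total bilirubin in the chemistry panel. Section 15.3 governs immune-related liver toxicity independently of criterion 7. Section 6.3.1 stops GM-CSF after related Grade 4 toxicity, apart from brief AST/ALT elevation. Section 6.1.5 bases continuation partly on laboratory results. This also stands, but these are monitoring and toxicity rules and do not replace the eligibility limit. In the text available, criterion 7 is the only explicit numeric bilirubin limit for repeat embolization.

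A third reply is that the 5 × ULN footnote is a poor yardstick. It concerns delaying or stopping immunotherapy, most of the hepatic algorithm is a figure that cannot be seen here, and the comparison needs an assumed ULN. That is fair. The 27 to 40 figure is illustrative, and the conclusion rests on the 100-fold conversion alone.

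None of this makes the printed limit correct. A reading error from the PDF is also unlikely: the same unit appears in two places whose surrounding wording differs, and mg/dl is rendered properly for creatinine in both.

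**Conclusion.** The concern holds. The bilirubin limit is printed as 200 mg/dl where 2.0 mg/dl is evidently meant, a 100-fold error that appears in exactly two places. That the written limit excludes no one assumes no candidate has a serum bilirubin above 200 mg/dl; the documents give no patient range, but the assumption is safe. That 2.0 mg/dl was intended is an inference from the neighbouring units and the scale of the other liver limits, and is for the sponsor to confirm.

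The correction should be made because the limit is binding at entry and at each treatment. It is not a flaw in the statistical design: sample size, alpha, power, endpoints and analyses are untouched.

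**What to change.** Have the sponsor confirm the intended limit, then replace mg/ml with mg/dl for bilirubin in the Study Summary and in section 4.1, criterion 7. The correction can go in with the next amendment. It costs a unit change in two places, with no change to design or analysis.
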